8. NUMBER OF SUBJECTS

- *Indicate the total number of subjects to be accrued locally. If applicable, distinguish between the number of subjects who are expected to be pre-screened, enrolled (consent obtained), randomized and complete the research procedures.*
- *If your study includes different cohorts, include the total number of subjects in each cohort.*
- *If this is multisite study, include total number of subjects across all sites.*

We will enroll 78 patients in the event that we lose some to follow up or if patients decide to unenroll in the study. We don't foresee many patients being lost to follow up because all patients will be enrolled only until their first follow up visit. The historic rate of patient's not following up with the surgeons after ACL reconstruction is almost 0.

9. STUDY TIMELINES

- *Describe the duration of an individual's participation in the study*
- *Describe the duration anticipated to enroll all study subjects*
- *The estimated date of study completion*

Study Duration - 1 Year

Each Individual's Participation –up to 14 days, depending on the date of initial follow up visit after the procedure. After that, the patients will follow up with their respective surgeons at time points determined by the surgeon for routine follow up.

10. ENDPOINTS

- *Describe the primary and secondary study endpoints*
- *Describe any primary or secondary safety endpoints*

A participant is considered to have completed the study if he or she has completed all phases of the study including the last visit or the last scheduled procedure. The end of the study is defined as completion of the last visit or procedure which we defined as the initial follow up visit in the office and the final survey will be sent out 14 days after the indicated surgery.

11. RESEARCH PROCEDURES

- *Include a detailed description of all procedures to be performed on the research subject and the schedule for each procedure.*
- *Include any screening procedures for eligibility and/or baseline diagnostic tests*
- *Include procedures being performed to monitor subjects for safety or minimize risks*
- *Include information about drug washout periods*
- *If drugs or biologics are being administered provide information on dosing and route of administration*
- *Clearly indicate which procedures are only being conducted for research purposes.*
- *If any specimens will be used for this research, explain whether they are being collected specifically for research purposes.*
- *Describe any source records that will be used to collect data about subjects*
- *Indicate the data to be collected, including long term follow-up*

Screening evaluation will occur during the preoperative visit prior to surgery which generally occurs within 28 days prior to surgery. No separate screening is indicated in this study.

Patients will be asked to participate in the study if they are having ACL Reconstruction surgery with one of the orthopedic surgeons who is participating in the study. They will be informed and consented in the office or in the preoperative holding area prior to surgery.

Patients undergo ACL reconstruction at either Plainview, Franklin, Huntington, Long Island Jewish, or North Shore University Hospital.

Any medical condition that is present at the time that the participant is screened will be considered as baseline and not reported as an adverse event (AE). However,

if the study participant's condition deteriorates at any time during the study, it will be recorded as an AE.

Changes in the severity of an AE will be documented to allow an assessment of the duration of the event at each level of severity to be performed. AEs characterized as intermittent require documentation of onset and duration of each episode.

We will record all reportable events with start dates occurring any time after informed consent is obtained until 7 (for non-serious AEs) or 30 days (for SAEs) after the last day of study participation. At each study visit/call, we will inquire about the occurrence of AE/SAEs since the last visit/survey/call. Events will be followed for outcome information until resolution or stabilization.

[figure not shown]
Study procedures and evaluations

- All patients who are enrolled in this study will have been evaluated and determined to be a candidate for ACL reconstruction surgery. The indications for surgery, determination of need for surgery and physical examination determining this need are independent from the interventions and outcomes being assessed by this study.
- **Efficacy Assessment plan-** All patients will be sent surveys through REDCAP, which is a secure patient secure electronic data capture software on postoperative days 1,2,3,4, 7 and 14. And be assessed in person at the post-operative visit which usually falls between post op day 10-14 depending on weekend and convenience. They will be surveyed for primary and secondary outcomes . Primary outcome will be assessed using visual analog scale 0-10. Secondary outcomes; Opiate consumption, Sleep quality, disturbances in sleep, global health assessment through the SF-12, and knee function through IKDC pre operatively and POD 14. The patient will also be contacted via telephone on post-operative day 1, 2, 3, 4 and 7 to assess for adverse events.
- Screening evaluation will occur during the preoperative visit prior to surgery which generally occurs within 28 days prior to surgery. No separate screening is indicated in this study.
- Procedure for administering study intervention and follow-up procedures. The participant will be seen in the preoperative holding suite prior to surgery to ensure that the patient is still willing to undergo randomization for the study. The patient will then undergo randomization by a computer-based software and the anesthesiologist will be informed of the plan. The participant will undergo anesthesia at the discretion of the anesthesiologist per routine given the participant's clinical baseline. The participant will undergo ACL reconstruction based on the standard of care treatment. Following surgery but prior to leaving the operating room the anesthesiologist will place the adductor canal block and the catheter based on the participant's randomization under ultrasound guidance to ensure proper placement of the block. The participant will then undergo routine

post-operative care in the recovery suite with routine recovery room vital checks. For participants who are randomized to the continuous pump group, the pump will be assembled and filled by pharmacy and attached to the previously placed catheter while the participant is in the recovery room. Once the participants are awake and alert in the recovery room, a study investigator will review the study specifics again, including the surveys with written information on the questions that will be asked. They will also be given written instructions on how to use the continuous pumps and how to remove it. If the patient is uncomfortable removing it themselves, they can come to the office to have it removed. For participants who received a continuous pump the investigator will go over the function of the pump, troubleshooting, and how to remove the pump at home. All participants will be discharged home from the recovery room after they have met the routine discharge criteria following existing standard of care recovery room protocols. The patient will also be contacted via telephone on post-operative day 1, 2, 3, 4 and 7 to assess for adverse events.

- All data will be recorded in an encrypted database which is HIPPA and IRB compliant. All participant information will be labeled with a participant study identification number with no identifiable information documented.

Procedures	In Office visit/schedule	Study Day 1, Day of Operation	Study Day 2 (POD 1)	Study Day 3 (POD 2)	Study Day 4 (POD 3)	Study Day 5 (POD 4)	Study Day 8 (POD 7)	Final Study Day, in office visit (POD 10-14)
Informed consent	X							
Demographics	X							
Medical history	X							
Randomization	X							
Administer study intervention		X						
Physical exam (including height and weight)	X	X						X
Preoperative Workup per standard protocol	X							
Pregnancy test ^b		X						
Adverse event review and evaluation	X		X X X X X					
MRI/Imaging assessment	X							
Online RedCAP Surveys (VAS, sleep disturbance, Opioid Consumption)	X	X X X X X X X X						

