23. CONSENT PROCESS

If obtaining consent for this study, describe:

- *Who will be obtaining consent*
- *Where consent will be obtained*
- *Any waiting period available between informing the prospective participant and obtaining consent*
- *Steps that will be taken to assure the participants' understanding*
- *Any tools that will be utilized during the consent process*
- *Information about how the consent will be documented in writing. If using a standard consent form, indicate such.*
- *Procedures for maintaining informed consent.*

The informed consent will be attached

- Who will be obtaining consent
 - Consent will be obtained by the Principal Investigator or one of the individuals that have been approved by the IRB to obtain consent.
- Where consent will be obtained
 - Consent will be obtained in the Ambulatory Surgery unit prior to surgery or at the preoperative visit in the office by one of the IRB approved consenting investigators. Patients will be given the information on the study and it will be reviewed with them prior to obtaining consent.
- Any waiting period available between informing the prospective participant and obtaining consent: The orthopedic surgeon can

inform the patients of the study at the pre-operative office visit to give them time to think about it before obtaining consent in the ambulatory surgery unit. This will allow patients a period of time to think about the pros and cons of participating in this research study which will be determined on the day of surgery preoperatively.

- Steps that will be taken to assure the participants' understanding
 - We have attached patient handouts in our protocol and IRB form to give patients a full understanding of the study plans, interventions, risks and benefits of each.
 - In addition, we will go over this information with the patient in person to confirm that they understand the goals of the study and the potential benefit to the patient.
- Any tools that will be utilized during the consent process
 - Informed consent documentation
- Information about how the consent will be documented in writing. If using a standard consent form, indicate such.
 - We will be using a standard consent form which we have designed and included in our IRB submission.
- Procedures for maintaining informed consent.

Signed informed consent forms will be maintained in a secure office with limited access.

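### The schedule table randomises at the office visit while the Section 11 text randomises in the holding suite on the day of surgery; the order of consent, pregnancy test, willingness check and randomisation needs to be stated once

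*Combined protocol and SAP*

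**What the plan says.** Two parts of Section 11 (Research Procedures) give different times for randomisation.

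- **Text.** The patient is seen in the holding suite before surgery "to ensure that the patient is still willing to undergo randomization for the study". The next step is: "The patient will then undergo randomization by a computer-based software and the anesthesiologist will be informed of the plan". Anaesthesia, surgery and then the block follow.
- **Schedule table.** The row "Randomization" has a single X, in the office-visit column. The row "Informed consent" has its single X in the same column. The row "Pregnancy test" has its X one column later, under the day of operation.

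On the interval between the two, Section 11 states: "Screening evaluation will occur during the preoperative visit prior to surgery which generally occurs within 28 days prior to surgery".

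Consent is also placed differently in different sections. Section 11 says: "They will be informed and consented in the office or in the preoperative holding area prior to surgery". Section 23 says: "Consent will be obtained in the Ambulatory Surgery unit prior to surgery or at the preoperative visit in the office". It adds that patients may hear of the study at the office visit and decide on the day of surgery. Section 12 mentions only the preoperative visit.

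Section 12 gives the allocation ratio, the stratification by hospital and the permuted blocks. It gives no time point for randomisation and leaves further procedural detail until after approval. It defines the intention-to-treat (ITT) population as everyone randomised. Its sample size paragraph makes no allowance for drop-out.

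**The concern.** Sites at five hospitals and the team building the randomisation system have two incompatible instructions for a core step, and nothing else in the plan settles which applies.

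If the table is followed, two checks come too late. Criterion 10 rests on a test done on the day of surgery. Criterion 14 (reconsideration) has no time point of its own, but the willingness check that would reveal a change of mind is in the holding suite. A patient who fails either check would already belong to the ITT population. The analysis must then either carry a randomised patient who may have no postoperative data or drop one contrary to its own definition.

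Patients who sign on the day of surgery have no valid place in the table at all, because the only randomisation tick precedes their consent.

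The trial is open-label. A patient randomised weeks ahead could know the arm when deciding whether to go on, so losses need not be balanced between arms. The documents do not say whether the arm would be disclosed that early.

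**Working it through.** **1. Is the table reading sound?** The table came through text extraction and is damaged in places: the adverse-event and survey rows have several X marks run together. The rows that matter here are intact. Consent, demographics, medical history and randomisation each have one X in the first column. Study intervention and pregnancy test each have one X in the second. The extraction therefore separates the office visit from the day of operation.

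**2. Order of steps under each instruction**

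| Step | If the table is followed | If the Section 11 text is followed |
|---|---|---|
| Consent at the office | Before randomisation is possible (same visit) | Before randomisation |
| Consent on the day of surgery | Patient cannot be randomised as scheduled | Compatible, if signed first |
| Willingness check | After randomisation | Before randomisation |
| Pregnancy test | After randomisation | Order not stated |

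The last cell is uncertain. The pregnancy row carries a footnote whose text is not available, and a figure in the section is not shown.

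**3. The plan's own sample size.** Inputs from Section 12, Sample Size Justification: difference 2 points, SD 2.5, two-sided α 0.01, 39 per group, 80% power on any single day, two-sample t-test.

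- Standardised difference: 2 / 2.5 = 0.8.
- Non-centrality: 0.8 / √(1/n₁ + 1/n₂). With 39 and 39 this is 3.533.
- Degrees of freedom: 39 + 39 − 2 = 76; critical t = 2.642.
- Power from the non-central t distribution: 81.0%.
- The exact solution is 38.19 per group, which rounds up to 39. The stated figure reproduces, with little to spare.

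**4. Illustration of losses.** The documents give no rate for positive tests or for reconsideration, so the counts below are assumptions.

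| Patients with data (arm 1 / arm 2) | Total lost | Single-day power |
|---|---|---|
| 39 / 39 | 0 | 81.0% |
| 39 / 38 | 1 | 80.4% |
| 38 / 38 | 2 | 79.8% |
| 39 / 37 | 2 | 79.7% |
| 37 / 37 | 4 | 78.4% |
| 36 / 36 | 6 | 77.0% |

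These follow the protocol's single-day t-test. The planned analysis opens day-by-day comparisons only after a significant treatment-by-day interaction, so they are not the power of the whole procedure.

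**The case against.** The strongest reply is that the Section 11 text is explicit and ordered: check willingness, randomise, tell the anesthesiologist. Section 23 also expects the decision on the day of surgery. On this view the table holds a misplaced tick, and harm follows only if staff obey the table against the text. In addition, Section 16 already follows patients who withdraw (unless they decline contact) and those not treated as allocated, and keeps patients withdrawn after treatment in their randomised group; Section 18 treats failed catheter placement by intention to treat. No general change to the ITT rule is needed.

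Much of this stands. It does not remove the point, because site staff commonly work from the schedule, Section 12 is silent on timing, and follow-up rules cannot supply outcomes from a patient who has none or declines contact.

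Some stronger readings are not supported:

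- A reader might infer that the schedule puts consent after randomisation. It does not: both are ticked at the same visit. The conflict appears only when the table is read with the day-of-surgery consent in Sections 11 and 23.
- A reader might assume that a positive pregnancy test cancels surgery, so that no outcomes can exist. Criterion 10 excludes the patient from the study; the available text does not say what happens to the operation.
- A reader might infer bias because the anesthesiologist knows the arm before giving anaesthesia. No size can be derived, and Section 12 already says that physicians cannot be blinded.

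**Conclusion.** The contradiction is real and sits in operative text. It should be corrected before randomisation is built, because it governs when a patient enters the ITT population and whether consent and eligibility are settled first.

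The numerical effect is small. Two patients lost take single-day power from 81.0% to 79.7–79.8%, and six (three per arm) to 77.0%, all with assumed counts. The trial would not be materially underpowered for this reason alone. The case for acting is that the losses are avoidable and the plan has no drop-out allowance to absorb them.

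The conclusion assumes that the extracted column positions are right, which the neighbouring rows support. The order of pregnancy test and randomisation under the Section 11 text is less certain, given the missing footnote and figure.

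**What to change.** - **Schedule table:** move the randomisation tick to the day-of-operation column, and add a day-of-operation tick to the consent row.
- **Section 11:** state one order: consent signed; eligibility checks complete, including the pregnancy test result where applicable; willingness confirmed; then randomisation in the Biostatistics Randomization Management System.
- **Section 12:** align the consent sentence with Sections 11 and 23, so that it covers the office visit or the day of surgery, in either case before randomisation.
- **Criteria 10 and 14:** reconcile their timing with Section 16, which lets an investigator discontinue or withdraw a patient for pregnancy or for an exclusion criterion that is new or was not recognised before. Limiting these criteria in Section 7 to the period before randomisation would leave that text unreconciled, so no such edit is proposed.

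The cost is two table cells, two sentences and a check of Section 16. No new procedure is needed, since the Section 11 text already randomises on the day of surgery. The one practical demand is that the pregnancy result, where applicable, is available before randomisation.

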12. STATISTICAL ANALYSIS

- *Describe how your data will be used to test the hypotheses.*
- *State clearly what variables will be tested and what statistical tests will be used.*

- *Include sample size calculations.*
- *If this is a pilot study, state which variables will be examined for hypothesis generation in later studies.*

Blinding:

Due to the nature of the intervention (bolus block, continuous infusion pump), it is not possible to blind the physicians or patients.

Consent:

Consent will be obtained during the preoperative visit, prior to surgery.

Randomization:

Subjects will be randomly assigned in a 1:1 ratio to either bolus block or continuous catheter. The randomization will be stratified by hospital (Plainview, Franklin, Huntington, Long Island Jewish, or North Shore University Hospital).

The Biostatistics Unit will develop a randomization procedure using a permuted block design within the Biostatistics Randomization Management System (BRMS).

Additional details of the procedure, including required record keeping, will be further developed upon approval of this protocol. The Biostatistics Unit has extensive experience in implementing and in producing detailed documentation for such procedures.

Intention to Treat (ITT):

All analyses will be carried out according to the ITT principle. The ITT population will be all subjects randomized, regardless of what treatment they actually received. All patients will be analyzed in the group to which they were randomized.

Statistical Considerations:**Specific Aims:**

To compare the efficacy of two postoperative pain control methods (bolus block, continuous catheter) in patients undergoing ACL reconstruction.

Primary Outcome

Outcomes measured on post-operative days 0, 1,2,3,4,7, and at the post-operative follow-up visit. (Outcomes for days 0, 1,2,3,4, and 7 will be obtained via email and electronic surveys . Outcomes for the post-operative follow-up visit will be measured during the postoperative visit which takes place between days 10 and 14. This will be referred to as "Day 10").

- Pain Control

- Maximum pain will be measured on a scale of 0 to 10, where 0 represents no pain and 10 represents the worst possible pain. Patients will report the maximum pain felt in the 24 hours
- Current pain will be measured on a scale of 0 to 10, where 0 represents no pain and 10 represents the worst possible pain.
- Daily opioid consumption (expressed as morphine equivalents).

Secondary Outcomes

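### The anesthesiologist learns the arm before a discretionary anesthetic, although the arms differ only after surgery; releasing the allocation at the end of surgery would close this route to unequal background analgesia

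*Combined protocol and SAP*

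**What the plan says.** Section 11 (Research Procedures, administering the study intervention) sets out this order.

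1. Before surgery: "The participant will be seen in the preoperative holding suite prior to surgery to ensure that the patient is still willing to undergo randomization".
2. Next: "The patient will then undergo randomization by a computer-based software and the anesthesiologist will be informed of the plan".
3. Anesthesia: "The participant will undergo anesthesia at the discretion of the anesthesiologist per routine given the participant's clinical baseline".
4. The ACL reconstruction is performed as standard of care.
5. Then: "Following surgery but prior to leaving the operating room the anesthesiologist will place the adductor canal block and the catheter based on the participant's randomization".
6. For the pump arm, "the pump will be assembled and filled by pharmacy and attached to the previously placed catheter while the participant is in the recovery room".

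The schedule table in the same section marks randomization at the office visit. That conflicts with step 2, but it is also before surgery.

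Section 12 (Blinding) says that, because of the nature of the two interventions, "it is not possible to blind the physicians or patients". Its primary-outcome list covers maximum pain, current pain and daily opioid consumption from day 0. Sections 4 and 11 start efficacy assessment at postoperative day 1 and class opioid use as secondary. The Section 12 model for the primary outcomes contains pain control method, day, their interaction and site.

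**The concern.** Until the block or catheter is placed, both arms are meant to receive the same care, and the protocol gives no reason for the anesthesiologist to know the arm before then. During that period the anesthesiologist selects the anesthetic and any intraoperative analgesia. A clinician who expects a single injection to wear off might supplement it more generously, or might give less to a patient going home with a pump. Either habit would add a second treatment difference to the randomized one.

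At stake are the early pain and opioid comparisons. Intraoperative analgesia is not recorded as study data, so the analysis could neither detect an imbalance nor adjust for one. A spurious early difference could also feed the method-by-day interaction, which decides whether day-by-day comparisons are made at all.

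**Working it through.** **The order of events.** Steps 2 to 5 above show that disclosure comes before anesthesia and the intervention comes after surgery. The interval between them is the whole anesthetic and operation. Three safeguards could protect that interval:

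- *Withholding the allocation until the end of surgery.* Section 11 does the opposite. Section 12 defers further randomization details to a later stage and is silent on release time.
- *Standardizing intraoperative analgesia.* The only limit is that anesthesia follows routine and the patient's clinical baseline.
- *Recording it and adjusting for it.* It is not among the outcomes or the schedule items, and the Section 12 models adjust for site only.

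None of the three is present.

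**The plan's own figure (Section 12, Sample Size Justification).** Inputs: difference 2 points, SD 2.5, two-sided alpha 0.01, two-sample t-test, 39 per group.

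- Standard error of the difference = SD × √(2/n) = 2.5 × √(2/39) = 0.566.
- Noncentrality = 2 / 0.566 = 3.53, with 2 × 39 − 2 = 76 degrees of freedom and critical value 2.642.
- Power from the noncentral t distribution = 81.0%. At 38 per group it is 79.8%, so 39 is the smallest size that reaches 80%. The plan's figure reproduces.

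**Illustration of size (assumed; the documents give no bias figure).** Suppose a fraction *f* of single-shot patients receives extra analgesia worth 1 point on the 0-10 scale. The between-group difference then shrinks by *f* × 1. With *f* from 10% to 50%, the loss is 0.1 to 0.5 points.

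| Remaining difference | Noncentrality | Single-day power |
|---|---|---|
| 2.0 (no bias) | 3.53 | 81.0% |
| 1.9 (*f* = 10%) | 3.36 | 76.0% |
| 1.75 (*f* = 25%) | 3.09 | 67.3% |
| 1.5 (*f* = 50%) | 2.65 | 50.6% |

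If instead there is no true effect and unequal care creates a shift in either direction, the single-day rejection rate at alpha 0.01 rises from 1% to 1.7% (0.25 points), 4.4% (0.5 points) or 19.8% (1 point).

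**Limits of the illustration.** The 2-point planning difference comes from day 3 pain in a shoulder-surgery study. The days most exposed here are day 0 and day 1, so the table applies a borrowed effect to those days. It does not estimate lost power on the day that anchored the design.

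**The case against.** The strongest reply is that the trial is openly unblinded, that anesthesia is tied to routine and clinical baseline rather than to arm, and that any effect would be confined to one or two of the six or seven time points. Much of this stands. The wording about routine and baseline is a real limit on discretion, though a soft one. Later days are less exposed. Day 0 appears only in the Section 12 outcome list, so exposure of the primary outcome depends partly on which list governs. The mechanism in the table, extra analgesia for the single-shot arm, would work against the superiority hypothesis rather than for it.

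The open-label statement does not answer the point. Its reason, the nature of the interventions, applies from block placement onward and does not explain why the arm must be known during the operation.

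A reader might infer several stronger claims that the documents do not support:

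- *That the early results will be biased, or biased in a known direction.* The documents show only that care can differ by arm.
- *That the surgical team also knows the arm during the operation.* Section 11 says only that the anesthesiologist is told.
- *That keeping cases altered during surgery under intention to treat is itself a bias.* Retaining them protects the randomized comparison.
- *That late disclosure costs nothing or makes the trial blinded during follow-up.* It has logistical costs, no pharmacy lead time is documented, and recovery staff and patients will still know the arm.

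**Conclusion.** The concern holds as an avoidable weakness in design. Disclosure comes earlier than the protocol gives any reason for, the intervening anesthetic is discretionary, and no safeguard covers the gap. Confidence is high about the sequence and low about its consequences, because the size and direction of any bias are unknown. The power range of 76.0% to 50.6% rests on an assumed 1-point effect in 10% to 50% of single-shot patients, and on applying the planned 2-point difference to the earliest days. Exposure is mainly at postoperative day 1, and at day 0 if the Section 12 list governs. The sample size is not in question. The change should be made because it is simple, and because the planned data could not repair an imbalance afterwards.

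**What to change.** Keep consent and confirmation of willingness in the holding suite. Amend the Section 11 procedure so that the Biostatistics Randomization Management System draws and releases the allocation only when surgery is complete, just before the adductor canal procedure, with pharmacy notified at the same moment. Correct the schedule table, which marks randomization at the office visit, to agree. State the release time in the randomization details that Section 12 leaves to be developed.

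The cost is protocol wording and a later call to the randomization system. In practice a catheter kit must be at hand in every case, and pharmacy has less notice to fill the pump, although the pump is attached only in the recovery room. A site that cannot work this way should at least record intraoperative analgesia and report it by arm.

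The change closes only the intraoperative route to unequal care. Recovery care and self-reported outcomes stay unblinded, and the report should say so. It does not alter the sample size, and no anesthetic or analgesic regimen is proposed here.
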